6.3.2 Summary Statistics

Data will be summarised by means of summary statistics. For continuous data the following summary statistics will be presented: number of observations, mean, standard deviation (SD), minimum, Q1, median, Q3 and maximum. 95% CI of the mean will also be presented for efficacy and safety data. Change from baseline to each post-baseline visit will be also described using descriptive statistics. Categorical data will be presented as counts and percentages.

Summary statistics will be presented by treatment group and visit, as applicable.

Certain presentations (withdrawals, patient exclusion from datasets, baseline and background characteristics and primary efficacy data) may be broken down by study center, if relevant.

All data collected during study follow-up will be displayed and analyzed according to the actual visit data in the eCRF.

6.3.3 Patient/Patient Data Listings

Data collected in the eCRF will generally be listed. eCRF check questions and reminders will not be listed.

Listings will be sorted by study center, patient number, visit (where applicable) and time point (where applicable).

All derived data will be presented in the corresponding data listings.

6.3.4 Demographic and Other Baseline Characteristics

Patient disposition, demographic data and other baseline data will be listed and presented using summary statistics.

Demographic data:

Date: 09-JUL-2021

Sponsor: Laboratorios Salvat, S.A. Study Code: CLOBOF3-16IA01 NCT No.: NCT04246801

Age, gender, ethnicity, race, weight (pounds), height (inches) and BMI will be summarized by treatment regimen and overall. SAF, FAS and PP population will be used for this presentation.

Relevant Medical History:

Medical history data will be coded according to the Medical Dictionary for Regulatory Activities (MedDRA), the latest versionMedical history will be summarized for the SAF by treatment regimen and overall on a per-patient basis (e.g., if a patient reported the same event repeatedly the event will be counted only once at the specific level of display). Absolute counts (n) and percentages (%) will be presented for the number of patients with at least one Medical History event, and per System Organ Class (SOC) and per Preferred Term (PT) within SOC.

A listing will present all history-related data for the SAF.

Other clinical baseline characteristics:

Urine pregnancy test results and cataract diagnosis date and study eye will be listed for the SAF. Patient disposition will be presented, based on individual study examination dates and end of study status. A listing will be provided (if applicable) for discontinued patients.

6.3.5 Primary Efficacy analysis

The primary efficacy endpoint in this clinical trial is the proportion of patients with anterior chamber cell grade of "0" (absence of cells) compared to placebo at Day 8.

The statistical hypothesis that will be tested for primary efficacy is described as:

- Null Hypothesis (H_0): The difference in proportion of patients with anterior chamber cell grade of "0" at Day 8 between treatment regimes = 0.
- Alternative Hypothesis (H₁): The difference in proportion of patients with anterior chamber cell grade of "0" at Day 8 between treatment regimes ≠ 0.

The aim of the primary analysis of this study is to assess the superiority of clobetasol propionate ophthalmic nanoemulsion 0.05% compared to placebo with respect to the primary efficacy endpoint. The primary analysis will be based on a single study eye for each patient. Each patient's study eye will be defined as the surgery eye.

A Chi-Square test will be employed to test the proportion of study eyes with complete clearing of anterior chamber cells (count cell = 0) at Visit 3 (Day 8 \pm 1 day) without receiving rescue medication as compared between clobetasol propionate ophthalmic nanoemulsion 0.05% dosed QID and placebo dosed QID. The proportion of eyes with absence of cells (anterior chamber cell grade=0) together with its 95% confidence interval (CI) will be presented. Analysis will be conducted both in FAS and PP to test the robustness of the results.

6.3.6 Secondary Efficacy Analyses

6.3.6.1 Key Secondary Efficacy Analysis

The key secondary efficacy endpoint is the proportion of patients with VAS pain score of "0" (no eye pain) compared to placebo at Day 8.

The key secondary analysis will be based on a single study eye for each patient. Each patient's study eye will be defined as the surgery eye.

Sponsor: Laboratorios Salvat, S.A. Study Code: CLOBOF3-16IA01

NCT No.: NCT04246801

A Chi-Square test will be performed to test the proportion of study eyes with no pain (VAS = 0) at Visit 3 (Day 8 ± 1 day) without receiving rescue medication as compared between clobetasol propionate ophthalmic nanoemulsion 0.05% dosed QID and placebo dosed QID. The proportion of eyes with no pain together with its 95% confidence interval (CI) will be presented.

Analysis will be conducted both in FAS and PP to test the robustness of the results.

6.3.6.2 Secondary Analysis

The secondary efficacy endpoints are described in Section 3.2. All secondary efficacy endpoints defined in this section will be analysed as exploratory.

For categorical variables, a summary of these endpoints will be presented at each specified timepoint by treatment group and will include the number and percentage of each category with the 95% CI. A chi-square test or Fisher Exact test, as appropriate will be performed to compare proportions between treatments at each timepoint.

For continuous variables: VAS photophia, Snellen best-corrected visual acuity (BCVA) score and VAS pain score, a summary of these endpoints will be presented at each specified timepoint by treatment group. Change from baseline will be derived and presented in the same way.

For variables: Anterior chamber cell grades, anterior chamber flare grades, severity of signs of ocular inflammation and eye discomfort grades categorical and continuous summary statistics will be presented, changes from baseline will also be derived and will be presented as increase, decrease or not change table. In the same way, a table with 2 categories: Improvement and no improvement (increase+no change) will be presented. A chi-square test or Fisher Exact test will be performed to compare proportions between treatments:

Change from baseline to Day 3		
Anterior Chamber Cell Grade	IMP	Placebo
Decrease (Improvement)	n (%)	n (%)
No change	n (%)	n (%)
Increase (Worsening)	n (%)	n (%)
P value chi-square or Fisher	p-v	value
Improvement	n (%)	n (%)
No Improvement	n (%)	n (%)
	p-v	/alue

No Improvement = increase + no change

For the variables mentioned above, to see the proportion of patients with different grades, a descriptive table like the following will also be built, no statistical inference will be made:

Grade	IMP			Placebo		
Grade	Baseline	Day X	Change	Baseline	Day X	Change
0	n (%)	n (%)	(%)	n (%)	n (%)	(%)

Date: |09-JUL-2021|

Sponsor: Laboratorios Salvat, S.A. Study Code: CLOBOF3-16IA01 NCT No.: NCT04246801

0.5+	n (%)	n (%)	(%)	n (%)	n (%)	(%)
1+	n (%)	n (%)	(%)	n (%)	n (%)	(%)
2+	n (%)	n (%)	(%)	n (%)	n (%)	(%)
3+	n (%)	n (%)	(%)	n (%)	n (%)	(%)
4+	n (%)	n (%)	(%)	n (%)	n (%)	(%)

Between treatment comparison of the evolution over time will be analysed using a Restricted Maximum Likelihood (REML)-based repeated measures approach (Mixed Model Repeated Measures [MMRM]). The model for analysis will include the change from baseline as a dependent variable, the baseline score as a cavariate, the categorical fixed effects of treatment (IMP, Placebo) and visit and the interaction treatment*visit. An unstructured (co)variance structure will be used to model the within-patient errors. If this analysis fails to converge, alternative covariance structures will be tested. Akaike's information criterion will be used to determine the best fit (smaller AIC).

If it is not possible to apply a MMRM due to the non-normality of the variable, the Mann Whitney Wilcoxon test will be performed.

Secondary efficacy analyses will be performed on the FAS population.

The PP population set will be also tested to confirm the robustness of the secondary analyses.

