9.1.1 Sample Size

A two group $\chi 2$ test with a 0.05 two-sided significance level will have 80% power to detect the difference between a proportion with complete resolution of anterior chamber cells in the active group of 0.22 and the placebo group proportion of 0.07 (odds ratio of 3.747) when the sample size is 202. Considering a 4% lost to follow-up rate a final sample size of 210 patients will be required (140 clobetasol, 70 placebo, in a 2:1 randomization ratio).

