6.4 Level of Significance, Multiple Comparisons and Multiplicity

All statistical hypotheses will be two-sided and will be performed using a 5% significance level. No adjustment for multiple comparisons or corrections for multiplicity are foreseen.

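### Grade changes in cells, flare, signs and discomfort are tested only by direction, with unordered tests that ignore baseline grade; one baseline-adjusted ordinal test would use the same data better

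*SAP*

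**What the plan says.** The grades are ordered: six levels for cells, five for flare, and four each for the five signs and for discomfort (SAP 3.1 and 3.2). For all of them, SAP 6.3.6.2 states that "changes from baseline will also be derived and will be presented as increase, decrease or not change table". A second table merges increase and no change into no improvement. On these tables, "A chi-square test or Fisher Exact test will be performed to compare proportions between treatments", and the layout shown has one p-value for each of the two tables.

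The same section describes a grade-by-grade table at baseline and visit, explicitly without inference. The MMRM paragraph, with its Mann-Whitney fallback, does not name its variables. SAP 6.5 ties MMRM to the continuous endpoints, and the only MMRM tables that can be read in the output list are photophobia VAS, visual acuity and pain VAS (14.2.12 to 14.2.14). No ordinal test is named for any graded variable.

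On status, the SAP says "All secondary efficacy endpoints defined in this section will be analysed as exploratory". On error control, SAP 6.4 says "All statistical hypotheses will be two-sided and will be performed using a 5% significance level" and foresees no multiplicity adjustment.

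**The concern.** Three kinds of information are dropped before the test is run.

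- **Size.** A fall from 3+ to 0 counts the same as a fall from 3+ to 2+. Yet one listed endpoint is change in the severity of signs, which direction alone does not measure.
- **Order.** The three-category chi-square treats decrease, no change and increase as unordered labels and spends 2 degrees of freedom.
- **Baseline.** Inclusion criterion 3 requires at least 5 cells, so every eligible patient starts at 0.5+ or above. A patient at 0.5+ can improve only by clearing completely, while one at 3+ improves by reaching 2+. No criterion sets a minimum for flare, signs or discomfort, so patients at grade 0 there enter the no-improvement row whatever happens.

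At stake is the efficiency and readability of the tables that support the secondary inflammation and discomfort objectives. A real shift could go unnoticed where an ordinal test on the same data would show it.

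**Working it through.** **1. The plan's own figure.** Protocol 9.1.1 describes a chi-square "test with a 0.05 two-sided significance level will have 80% power to detect the difference" with an active "group of 0.22 and the placebo group proportion of 0.07 (odds ratio of 3.747) when the sample size is 202", allocated "140 clobetasol, 70 placebo, in a 2:1 randomization ratio". With a 2:1 ratio, the pooled rate is (2×0.22 + 0.07)/3 = 0.17.

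n(placebo) = [1.960×√(0.17×0.83×1.5) + 0.8416×√(0.22×0.78/2 + 0.07×0.93)]² / 0.15² = [0.9017 + 0.3269]² / 0.0225 = 67.1

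The total is 3 × 67.1 = 201.3, so 202 (204 if the placebo arm is first rounded up to 68). Power at 135:67 is 80.0%. The odds ratio is (0.22/0.78)/(0.07/0.93) = 3.747, and 202/0.96 = 210.4. The plan reproduces, but it concerns only grade 0 for cells at Day 8. No power is stated for the grade-change tests.

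**2. Assumptions needed (not in the documents).** Simulated trials of 140:70, 1,000 per scenario, latent-normal grades, baseline-to-Day 8 correlation 0.3 or 0.6. The treatment effect is a common odds ratio: each placebo cumulative proportion c becomes c·OR/(1 − c + c·OR). With c = 0.07 this gives 0.22 at OR 3.747 (the plan's rate) and 0.14/1.07 = 0.13 at OR 2.0. Assumed mixes, in %:

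- Cells, baseline 0.5+ to 4+: 10/35/35/15/5, 30/40/20/8/2 or 5/20/40/25/10. Placebo Day 8, grades 0 to 4+: 7/33/35/17/6/2 or 7/20/33/25/10/5.
- Flare: baseline 20/40/30/8/2, placebo Day 8 40/35/18/5/2.
- Four-grade sign: baseline 20/45/30/5, placebo Day 8 45/35/16/4.
- Sign mostly absent: baseline 60/25/12/3, placebo Day 8 70/20/8/2.

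**3. Power (%) at two-sided 0.05.** Cells show the range over 12 scenarios; the other rows show correlation 0.3 / 0.6. The last test compares Day 8 grade ranks after adjustment for baseline ranks. Loss is that test minus the three-category chi-square.

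| Variable, OR | 3-category chi-square | Improved yes/no | Wilcoxon on change | Baseline-adjusted ranks | Loss (points) |
|---|---|---|---|---|---|
| Cells, 2.0 | 36–71 | 41–72 | 55–83 | 76–88 | 16–43 |
| Flare, 2.0 | 40.2 / 54.0 | 35.6 / 48.6 | 46.5 / 62.9 | 73.2 / 83.6 | 33 / 30 |
| Sign, 2.0 | 38.6 / 52.1 | 35.7 / 50.1 | 45.2 / 60.5 | 70.2 / 80.0 | 32 / 28 |
| Sign mostly absent, 2.0 | 33.7 / 38.4 | 11.2 / 16.0 | 28.2 / 34.3 | 54.1 / 60.4 | 20 / 22 |
| Cells, 3.747 | 80–100 | 85–100 | 97–100 | about 100 | 0–20 |
| Flare, 3.747 | 88.7 / 96.0 | 79.6 / 91.9 | 90.9 / 97.9 | 99.8 / 99.9 | 11 / 4 |
| Sign, 3.747 | 84.5 / 94.0 | 78.1 / 90.9 | 89.2 / 96.9 | 99.5 / 100 | 15 / 6 |
| Sign mostly absent, 3.747 | 76.7 / 78.6 | 20.9 / 29.7 | 51.4 / 64.9 | 94.8 / 96.6 | 18 / 18 |

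For cells at 3.747, ten of the twelve losses are 11 points or less. The other two, 12 and 20, combine severe baselines with good placebo recovery. At 2.0, eight of the twelve lie between 16 and 32 points. Under no effect, all tests rejected in 5.0% to 5.9% of trials. Monte Carlo error is up to about 1.6 points.

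**4. Van Elteren stratified by baseline grade, OR 2.0.** Two further sets of runs at 140:70 under assumed grade mixes:

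- Cells: chi-square 47 and 65 rises to 75 and 86; in the other set, 46–64 rises to 76–84.
- Four-grade signs: 40 and 57 rises to 71 and 83; in the other set, 38–53 rises to 71–80.
- Signs mostly absent: 32 and 36 rises to 49 and 56; in the other set, 26–28 rises to 41–47.

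The gains run from about 15 points (26 to 41) to 33 (38 to 71). Type I error was about 4% to 7%.

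**5. Unadjusted Wilcoxon on grade change is not a dependable remedy.** For cells at OR 2.0 it gained 12 to 30 points in the runs of step 3, but little or nothing under other assumed mixes. For signs mostly absent it fell below the chi-square: 28–34 against 34–38 at OR 2.0, and 51–65 against 77–79 at 3.747.

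**6. Number of p-values.** Eight variables (cells, flare, five signs, discomfort) × 4 visits × 2 tables = 64 overlapping, unadjusted p-values per population. One test per variable and visit gives 8 × 4 = 32.

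**The case against.** The strongest case is that this is a choice of method on exploratory endpoints, not an error.

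- The Protocol (9.1.12) already names chi-square for categorical variables, and the cell, flare and discomfort endpoints are worded as proportions across grades. That is fair. It does not cover the endpoint on severity of signs, and the proportion-by-grade table is the one left without a test.
- Depth of response is partly tested elsewhere: cells at 0, at 1+ or less, and jointly with flare 0; discomfort at none. This stands for cells and discomfort. Flare enters only jointly with cells, and signs have only presence or absence.
- The improvement/no improvement test respects direction, and continuous summaries of the grades are shown. True, but that test still ignores size and baseline, and the summaries carry no test.
- Wilcoxon on grade change depends on the numeric spacing of the grades. That objection stands against it. It does not touch a test stratified by baseline grade: within a stratum, ranking the change and ranking the visit grade are the same thing.

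A reader might also infer that much of the power is lost whatever the effect, or that improvement nears a ceiling because most patients on both arms gain a grade. The documents support neither. They give no grade distributions, the loss for cells is mostly small at the planning odds ratio, and no improvement rate is stated for either arm. The loss also appears in scenarios where well under half of placebo patients improve.

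**Conclusion.** The point holds as a cheap improvement. The planned inference on graded change uses direction only, is unordered, and takes no account of baseline. For flare and sign severity, no other planned test uses the size of change.

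The size is conditional. Against a baseline-adjusted ordinal test the three-category chi-square gives up roughly 15 to 35 points at OR 2.0, and more in some cell scenarios. At 3.747 it gives up about 0 to 10 points for cells in most scenarios, and nearly 20 for signs mostly absent at baseline. These figures rest on assumed grade mixes and correlations and on a common odds ratio across all grade cuts, a pattern that suits ordinal tests. Outside cell grade 0 at Day 8, the value 3.747 is borrowed.

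It would be wrong to read this as a threat to the trial's main claims. The primary and key secondary analyses use other endpoints and are untouched. No bias or inflation of type I error of the planned tests is shown.

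**What to change.** In SAP 6.3.6.2, for each graded variable and each visit, name one baseline-adjusted ordinal test of the visit grade: van Elteren stratified by baseline grade, or a proportional-odds model with treatment and baseline grade. State in advance how sparse baseline grades are merged. Keep the three-category and two-category change tables as counts and percentages without p-values. Do not substitute an unadjusted Wilcoxon on grade change. State that MMRM and its Mann-Whitney fallback apply only to photophobia VAS, visual acuity and pain VAS.

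The cost is SAP wording and a different test in existing tables, using data already planned for collection. The downside is a p-value that cannot be read directly off a 2×2 table. If treatment codes have already been opened, report the ordinal analysis as post hoc, as Protocol 9.2 requires.

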2. INTRODUCTION

2.1 Background

Global estimates suggest that 94 million people are visually impaired because of cataracts, and of these, 20 million are blind (1). Because the incidence of cataracts increases with age, an increase in the elderly population will lead to a significant increase in cataract prevalence. Cataracts currently affect approximately 26 million Americans (2), and approximately 25% of people in the United States of America (US) aged 65 to 69 years have cataracts, a proportion increasing to more than 68% of those aged over 80 years (3).

Cataract surgery is one of the most common surgical procedures performed worldwide. In fact, in 2017, 3.8 million cataracts procedures were performed in the US. The range of different types of procedures in ophthalmic surgery is broad, and the profile and characteristics of patients are widely varied (healthy young children, elderly patients and patients with multiple concomitant diseases and even neonates). The phacoemulsification technique was introduced in the treatment of cataract in 1967 and gained acceptance in the early 1990s when safety and efficacy improved. The efficacy of the phacoemulsification technique and the increase in life expectancy are the reasons for the increasing number of procedures performed.

Despite of surgical advances, pain and inflammation after ophthalmic surgery continues to be a burden on both patients and physicians (4). Postoperative inflammation is manifested principally as bulbar and ciliary hyperemia, corneal edema and aqueous cells and flare. The treatment of postoperative pain is essential for hospitalized patients, but it is even more important for patients who are treated on an outpatient basis (5).

Although cataract extraction is common, little is known about postoperative recovery and pain after phacoemulsification with intraocular lens implantation. However, knowledge of the postoperative complaints associated with ophthalmic surgery is necessary because these complaints may delay recovery and may significantly influence quality of life after the procedure (6).

The postoperative pain after this procedure was studied and found that 55% of patients had no pain or discomfort postoperatively, 32% reported slight discomfort, 8% of patients experienced mild pain and only 5% suffered moderate to severe pain (5,7).

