5. STUDY POPULATION

5.1 Inclusion Criteria

Patients will be eligible for study participation if they meet all of the following criteria:

- 1) Male or female, age 18 years or older on day of consent
- 2) Patients with routine unilateral cataract surgery on the day prior to study randomization
- 3) Patients with at least 5 cells in anterior chamber on the first day after surgery (at Visit 1)
- 4) Willing and able to understand and provide written ICF (at Visit -1)
- 5) Women who satisfy one of the following:
 - a) Are of child-bearing potential who are not pregnant or lactating and who are either abstinent or sexually active on an acceptable method of birth control (methods that can achieve a failure rate of less than 1% per year when used consistently and correctly, like hormonal contraception (oral pills, implantable device, or skin patch), intrauterine device, bilateral tubal occlusion, or double barrier) for at least 4 weeks prior to Visit 1 and throughout the study (i.e., until Day 29),

OR

b) Are post-menopausal (have had no menstrual cycle for at least one year prior to Visit -1) or have undergone a sterilization procedure (bilateral tubal ligation, hysterectomy, hysterectomy with unilateral or bilateral oophorectomy or bilateral oophorectomy) at least 6 months prior to Visit -1

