14.2 EFFICACY DATA

Primary efficacy analysis

Table	Title	Pop	Top.Line
14.2.1.1	Percentage of patients with anterior chamber cell grade of "0" compared to placebo at Day 8	FAS	X
14.2.1.2	Percentage of patients with anterior chamber cell grade of "0" compared to placebo at Day 8	PP at Visit 3	
14.2.1.3	Percentage of patients with anterior chamber cell grade of "0" compared to placebo at Day 8	FAS non- RM	Х

Sponsor: Laboratorios Salvat, S.A. Study Code: CLOBOF3-16IA01 NCT No.: NCT04246801

Main Secondary efficacy analysis

Table	Title	Pop	Top.Line
14.2.2.1	Proportion of patients with VAS pain score of "0" (no eye pain) compared to placebo at Day 8.	FAS	Х
14.2.2.2	Proportion of patients with VAS pain score of "0" (no eye pain) compared to placebo at Day 8.	PP at Visit 3	
14.2.2.3	Proportion of patients with VAS pain score of "0" (no eye pain) compared to placebo at Day 8.	FAS non- RM	X

Secondary efficacy analysis

Table	Title	Pop	Top.Line
14.2.3.1	Proportion of patients with anterior chamber cell grade of "0" compared to placebo at Day 3, Day 15 and Day 29	FAS non- RM	X
14.2.3.2	Proportion of patients with anterior chamber cell grade of "0" compared to placebo at Day 3, Day 15 and Day 29	FAS	
14.2.3.3	Proportion of patients with VAS pain score of "0" (no eye pain) compared to placebo at Day 3, Day 15 and Day 29.	FAS non- RM	X
14.2.3.4	Proportion of patients with VAS pain of "0" compared to placebo at Day 3, Day 15 and Day 29.	FAS	
14.2.4.1	Change from Baseline to Day 3, Day 8, Day 15 and Day 29 compared to placebo in the proportion of patients with different anterior chamber cell grades. Improvement and no Improvement table.	FAS non- RM	
14.2.4.2	Change from Baseline to Day 3, Day 8, Day 15 and Day 29 compared to placebo in the proportion of patients with different anterior chamber cell grades. Descriptive table	FAS non- RM	
14.2.5.1	Change from Baseline to Day 3, Day 8, Day 15 and Day 29 compared to placebo in the proportion of patients with different anterior chamber flare grades. Improvement and no Improvement table.	FAS non- RM	
14.2.5.2	Change from Baseline to Day 3, Day 8, Day 15 and Day 29 compared to placebo in the proportion of patients with different anterior chamber flare grades. Descriptive table	FAS non- RM	
14.2.6.	Proportion of patients with anterior chamber cell grade of "≤0.5+" and flare grade of "0" compared to placebo at Day 3, Day 8, Day 15 and Day 29.	FAS non- RM	

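### On seven exploratory measures the SAP counts every patient at baseline grade 0 as not improved, which dilutes the between-arm difference by an amount the documents do not let us fix

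*SAP*

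**What the plan says.** SAP 6.3.6.2 (Secondary Analysis) treats anterior chamber cell grade, flare grade, severity of the signs of ocular inflammation and discomfort grade alike. Change from baseline is shown in three rows (decrease, no change, increase) with a p-value. Then "a table with 2 categories: Improvement and no improvement (increase+no change) will be presented", again with a p-value. A separate by-grade table is planned without inference. The output list in SAP 8.1 carries the rule to the individual measures, for example Table 14.2.5.1 on the "proportion of patients with different anterior chamber flare grades. Improvement and no Improvement table", and Tables 14.2.11.1, .3, .5, .7 and .9 for the five signs.

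On every one of these scales grade 0 is the lowest grade and means absence. Among these measures, entry sets a floor for cells only: "Patients with at least 5 cells in anterior chamber on the first day after surgery (at Visit 1" (Protocol 5.1). Neither Protocol 5.1 and 5.2 nor SAP 5 and 6.3.6.2 requires flare, a sign or discomfort at baseline, or limits the denominator of the Improvement tables to patients who have something to improve.

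SAP 6.3.6.2 labels all these endpoints exploratory.

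**The concern.** The shell in SAP 6.3.6.2 is drawn for cell grade. Five cells or more is grade 0.5+ or higher, so every eligible eye can improve. The same shell is then used for seven measures where that is not guaranteed: flare, chemosis, bulbar conjunctival injection, ciliary injection, corneal edema, keratic precipitates and discomfort.

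On these, a patient at grade 0 on Day 1 and Day 8 has had the best possible course, yet shares a row with a patient who stayed at severe and one who got worse. The three-row table has a related weakness, because its no-change row mixes 0-to-0 with persistent disease.

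At stake is how readable and sensitive these tables are: the improvement percentage partly measures how common the sign was at baseline, and a real difference among affected patients appears smaller than it is.

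**Working it through.** **1. The plan's own figure.** Protocol 9.1.1 states that the trial "will have 80% power to detect the difference between a proportion with complete resolution of anterior chamber cells" of 0.22 on active and a "placebo group proportion of 0.07 (odds ratio of 3.747) when the sample size is 202", at two-sided 0.05 and 2:1.
- Odds ratio: (0.22/0.78)/(0.07/0.93) = 3.747, as stated.
- Pooled rate: (2×0.22 + 0.07)/3 = 0.17.
- Placebo n (pooled-variance chi-square, no continuity correction): [1.96×√(0.17×0.83×1.5) + 0.8416×√(0.07×0.93 + 0.22×0.78/2)]² / 0.15² = 67.1. The total is 3 × 67.1 = 201.3, which rounds up to 202 (204 if each arm is rounded up). Power at 202 is 80.2%.
- 202/0.96 = 210.4, against the stated 210.

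The stated size is reproduced, so the same test formula is used below. This calculation covers the primary endpoint only; no power is stated for the seven measures.

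**2. Effect of the rule.** Let q be the share with baseline grade 1 or more, pT and pC the improvement rates among them, and p their pooled value, (2pT + pC)/3.
- SAP rule: compare q·pT with q·pC in 140 and 70 patients. The ceiling is q and the difference is q(pT − pC).
- Restricted test: compare pT with pC in 140q and 70q patients.
- Ratio of the two test statistics, SAP rule to restricted: approximately √[(1 − p)/(1 − qp)]. The loss depends on both q and p.

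**3. One case in full (assumed q = 0.45, pT = 0.80, pC = 0.60).**
- SAP rule: 0.36 vs 0.27, difference 0.09, pooled 0.33. Null SE = √(0.33×0.67×(1/140 + 1/70)) = 0.0688. Alternative SE = √(0.36×0.64/140 + 0.27×0.73/70) = 0.0668. Power = Φ[(0.09 − 1.96×0.0688)/0.0668] = 25%.
- Restricted: 63 and 31.5 patients, difference 0.20, pooled 0.733. Null SE = 0.0965, alternative SE = 0.1008. Power = Φ[(0.20 − 1.96×0.0965)/0.1008] = 54%.

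**4. Range.** All q and rates are assumptions. The pair 22% vs 7% is borrowed from the primary endpoint.

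| q | Improve, active vs placebo | Ratio of test statistics | Power, SAP rule | Power, restricted |
|---|---|---|---|---|
| 0.45 | 80% vs 60% | 0.63 | 25% | 54% |
| 0.45 | 50% vs 30% | 0.84 | 33% | 45% |
| 0.45 | 22% vs 7% | 0.95 | 40% | 44% |
| 0.90 | 80% vs 60% | 0.89 | 73% | 82% |

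Over a wider grid the relative loss runs from about 1% (q = 0.90, 22% vs 7%) to about 80% (q = 0.2 to 0.3, 95% vs 80%). Simulation of the Pearson chi-square agreed with the formula in the first row (0.256 and 0.546). With no true effect it gave rejection rates of 0.050 to 0.051 under both rules.

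The 140 and 70 are upper bounds, because SAP 8.1 places these Improvement tables in the set without rescued patients.

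**5. What else tests these measures.**
- Signs: presence or absence at each visit (14.2.9) and its change (14.2.10). Neither registers a fall from severe to mild; only 14.2.11 does.
- Discomfort: proportion with none at each visit. Here a 0-to-0 patient counts favourably.
- Flare: only jointly with cell grade (14.2.6 and 14.2.8).

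**The case against.** The proportion improved among all analysed patients is a legitimate, conservative summary. The test keeps its error rate, and chance imbalance in baseline grade 0 is already covered by it. The endpoints are exploratory, and the sample size was never meant to serve them. The three-row and by-grade tables let a reader see the grade-0 counts by arm. Restricting to baseline grade 1 or more asks a narrower question, with denominators that differ by sign and may be small.

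Most of this stands, and it limits the weight of the point. It does not remove it. Flare alone, and change in the severity of a sign, are tested only by this rule or by the three-row table, which has the related weakness. The restriction is also sound in design terms: Protocol 4.3.2.2 takes the baseline grades before the first dose.

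Two stronger readings are tempting. One is that the seven tests lose about half their power. A reader might start from Protocol 2.1, where "55% of patients had no pain or discomfort postoperatively, 32% reported slight discomfort", and set 55% at grade 0. That is background literature on pain and discomfort combined, in patients not selected for five or more cells. It says nothing about flare or the signs, and the documents give no improvement rates for any of the seven. A loss near half is one row of the table above. The other reading is that a true effect would be reported as absent. The companion analyses of sign presence and of no discomfort do not penalise grade 0, and the flare composites cover part of the rest.

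**Conclusion.** The point holds in a limited form. As written, the rule places every baseline grade-0 patient among the not improved on seven measures where grade 0 cannot decrease. It caps the improvement percentage, shrinks the difference in proportion to baseline prevalence, and costs power. The cost cannot be fixed from the documents. In the four illustrative cases it runs from 4 percentage points (40% against 44%) to 29 (25% against 54%), and these rest on assumed prevalence and improvement rates with the full 140 and 70 patients. False positives are not increased, and neither the primary nor the key secondary conclusion depends on these tables. Severity: minor.

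**What to change.** In SAP 6.3.6.2 and in the flare (14.2.5.1), sign-severity (14.2.11.1, .3, .5, .7, .9) and discomfort Improvement tables:
- Test improvement only among patients with baseline grade 1 or more, and show that n per arm.
- For patients at baseline grade 0, report by arm and visit how many remained at 0 and how many had new onset.
- In the three-row table, split the no-change row into remained at grade 0 and no change at grade 1 or more.
- Leave the cell-grade table as it is.

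The cost is SAP wording and table shells, with no new data. Denominators will vary by sign and may be small for rare ones; the Fisher option already in the SAP covers that.
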